Statistical Analysis Plan v4

Diet and risk of hip fracture in the UK Women's Cohort Study

[name], [name], and [name]

Oct 4th, 2021

NCT number:

1. The UK Women's Cohort

The dataset will use participant data from the pre-existing UK Women's Cohort Study (UKWCS). The cohort profile has been previously published [1].

2. Data cleaning

Potential outliers will be identified by considering their distance from the mean and their biological plausibility (e.g., energy intake < 500 or > 5000 kcal/day, or BMI < 10 kg/m²); participants with identified outliers will be excluded. Missing data will be coded consistently throughout the dataset. All data cleaning will be documented for transparency.

2.1 Exclusion criteria

Participants will be excluded from analyses for any of the following reasons:

- Not a resident of England
- Unable to link dietary and lifestyle data with hospital episode data (e.g. no NHS number provided and unable to match with records)
- Unreliable or missing nutrient or covariate data (e.g., $\geq 20\%$ of food frequencies missing)
- Had a hip fracture or osteoporosis before or on the date of recruitment

3. Exposures

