To explore potential associations between foods and beverages and hip fracture incidence, food and beverage intake variables in grams per day will be calculated by multiplying servings per day intake variables by standard portion weights, and summing relevant FFQ items. Food and beverage intake variables (grams/day) will be used to explore the effects of increment increases in intake on hip fracture risk, and to categorise participants into non-consumers (if > 1000 participants in this category) and levels of intake for all exposure variables, ensuring equal distribution of the population size among categories where possible. For intakes of milk, tea, coffee, and tea and coffee combined, increment increases and categories of intake will be defined by glasses and cups per day using standard sizes with the lowest exposure category as the reference group. For fruits, vegetables, and fruits and vegetables combined, categories will be defined to compare intakes below and above the

recommended five-a-day (400 g/day) intake, which will be used as the reference category. All other food and beverage exposures will be split into thirds or quarters.

Nutrient variables will be derived by multiplying food and beverage intakes (g/day) by nutrient concentrations in each food or beverage item using McCance and Widdowson’s Food Composition database (5th edition) [2].

4. Outcomes

Participants will be followed up via record linkage to the NHS Hospital Episode Statistics up to 31 March 2019. The primary outcome will be hip fracture incidence (International Classification of Diseases, ICD-9 code 820, and ICD-10 codes S72-S72.2). Hip fracture cases will also be identified by hip replacements (ICD-10 code Z96.64). The timeframe will be person years until hip fracture incidence (or until end of study period or death in those without a hip fracture), calculated as age at time of event (or non-event) minus age at study entry.

5. Sample size

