The minimum detectable hazard ratio for the potential association between each primary exposure and hip fracture was estimated assuming a sample size of 26,300 (after applying exclusion criteria), an overall probability of hip fracture incidence of 3%, $p < 0.05$, and 80% power. For the dietary group analysis, a theoretical standard deviation of the exposure was calculated based on the percentage of participants in each category (Table 2). The minimum detectable effect of other primary exposures was calculated per standard portion size increase in intake using standard deviations of each exposure from the data in hand. Standard portion sizes were estimated from the Foods Standards Agency and previous UKWCS analyses [3, 4]. A standard portion size for total animal products was calculated by averaging standard servings of meat, fish, eggs, and dairy products.

Table 2: Minimal detectable hazard ratios for associations between primary exposures and hip fracture risk.

Exposure	SD	Minimum detectable HR
Dietary group (vegetarians vs non-vegetarians)	0.36	1.32
Fruit and vegetables (per 80 g increase)	300 g	0.98
Fruits (per 80 g increase)	227 g	0.97
Vegetables (per 80 g increase)	139 g	0.95
Total animal products (per 120 g increase)	248 g	0.95
Total meat (per 150 g increase)	81.2 g	0.84
Total fish (per 140 g increase)	28.3 g	0.61
Eggs (per 88 g increase)	18.6 g	0.63
Total dairy (per 105 g increase)	214 g	0.95

Tea and coffee (per cup increase)	2.17 cups	0.96
Tea (per cup increase)	2.01 cups	0.95
Coffee (per cup increase)	1.65 cups	1.06
Protein (per 25 g increase)	26.3 g	0.91
Calcium (per 300 mg increase)	365 mg	0.91
Vitamin D (per μg increase)	1.67 μg	0.94

1 cup of tea or coffee = 260 ml. SD = Standard deviation. HR = Hazard ratio. The SD for dietary group is theoretical and has arbitrary units.

6. Descriptive statistics

Baseline socio-demographic, anthropometric, diet, and lifestyle characteristics of the cohort were collected via questionnaire at baseline, and will be summarised (e.g. presenting their means and standard deviations) by: 1) dietary group (both for data-derived and self-identified dietary group); 2) total fruit and vegetable consumption; 3) total animal product consumption; 4) total tea and coffee consumption, and 5) protein, calcium, and vitamin D intakes, to report any differences in covariates (including co-exposures) between groups at baseline.

7. Statistical modelling

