7.1.1 Accounting for confounding

For all primary analyses, we will present age-adjusted, minimally adjusted, and fully adjusted models. Minimally adjusted models will be adjusted for the minimally sufficient set of confounders. Three directed acyclic graphs (DAGs) will be constructed using the online tool DAGitty, and following

available guidelines on the creation and reporting of DAG models to determine minimal adjustment sets in models of associations between hip fracture and 1) dietary patterns; 2) foods and beverages; and 3) nutrient intakes [7]. Confounders will be considered as covariates that are 1) risk factors of the outcome; 2) associated with the exposure; and 3) not caused by the exposure [8]. Confounders common to all research questions will likely include: age at baseline, ethnicity, socio-economic status, education, marriage, physical activity, smoking, alcohol, BMI (or height and weight), number of children, menopausal status, chronic disease at baseline, and fracture at baseline (non-hip). A list of likely confounders and their derivation is summarised in Supplementary Table 2. We will adjust for baseline chronic disease and fracture prevalence at sites besides the hip rather than excluding these subjects in minimally adjusted models to reduce the risk of selection bias that would result from excluding unhealthier subjects. Fully adjusted models will be further adjusted for competing exposures.

Energy intake will be adjusted for using the ‘all-components’ method for all analyses except dietary groups, for which energy intake could plausibly be a mediator, thus will remain unadjusted [9]. This method involves adjusting for all other individual components of energy intake besides the exposure at hand, and has been shown to produce the least biased and most precise estimand for relative and total causal effects [9]. For food and beverage exposures of interest, this will involve mutual adjustment for other major foods and beverages or food and beverage groups that might be associated with hip fracture incidence. For energy-contributing nutrient exposures of interest (macronutrients), this will involve mutual adjustment for other energy-contributing nutrients (e.g., saturated and unsaturated fat). For non-energy contributing nutrient exposures (micronutrients), this will involve adjustment for all energy-contributing nutrients, whilst avoiding over-adjustment as a result of high correlation between nutrients.

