7.3 Sensitivity analyses

For the dietary group analysis, we will present models with vegans and vegetarians separated. We will also compare risk estimates between self-identified and data-derived dietary groups. For all analyses, we will explore the potential mediating effect of covariates identified in DAG models as being associated with hip fracture incidence and plausibly caused by the exposure by adding each of these covariates to adjusted models independently. Models will be presented with and without adjustment for BMI. To reduce risk of bias due to changes in exposure over time, phase two dietary data (collected four years after baseline) will be compared with baseline dietary data. In cases of substantial exposure change over time (e.g., > 10% of participants changing their dietary group or primary exposure categories), models will be repeated using phase two data if there is sufficient power.

Additional sensitivity analyses will involve excluding cases occurring in the first five years of follow-up (to check for reverse causality), and excluding participants on long-term treatment for illnesses. All analyses will be performed using Stata. Two-sided p values < 0.05 will be considered statistically significant. We acknowledge that the large number of planned exposure-outcome association tests increases the risk of a type-2 error. However, the alpha value will not be restricted below $p < 0.05$ since secondary analyses (including most nutrient-hip fracture associations) will be exploratory, with only the primary analyses considered hypothesis-testing. All analyses performed and effect sizes computed will be presented in resulting manuscripts to avoid bias in selection of the reported result.

8. Missing data

Participants with missing data for an FFQ item will be considered non-consumers. Participants will be excluded from each specific analysis if they have missing data for any other variable required in that analysis. Techniques to impute missing dietary or covariate data will not be performed.

9. Timescales

Target analysis completion date (excluding manuscript preparations): Jan 2021.

10. References

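### Section 4 lets a hip replacement code identify a hip fracture case, but section 2.1 does not name prior hip replacement as a baseline exclusion, so an old replacement can be counted as an incident event

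*SAP*

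**What the plan says.** Section 4 (Outcomes) gives two routes to a case. The first is by fracture codes: "The primary outcome will be hip fracture incidence (International Classification of Diseases, ICD-9 code 820, and ICD-10 codes S72-S72.2"). The second is by replacement: "Hip fracture cases will also be identified by hip replacements (ICD-10 code Z96.64"). The second route carries no condition that the replacement be a first occurrence, that the operation be dated after recruitment, or that a fracture code accompany it.

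Time at risk is "calculated as age at time of event (or non-event) minus age at study entry".

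Section 2.1 (Exclusion criteria) removes at baseline any woman who "Had a hip fracture or osteoporosis before or on the date of recruitment". Hip replacement is not in the list. The section does not say which records establish a prior hip fracture, nor that the section 4 case definition applies to the exclusion.

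**The concern.** An incidence analysis should start with women who do not already carry the condition that will later define a case. Section 4 has two routes to a case, and section 2.1 explicitly clears only one of them. A woman with a replacement before recruitment is not excluded by the words of section 2.1. If the code first shows in her linked record at a later admission, nothing in section 4 stops that admission from becoming her event.

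Such an event would be wrong in kind and in date: her person-years would end at a hospital contact, not at a fracture. The primary outcome feeds every model in section 7. It also feeds the predicted incidences and absolute risk differences in section 7.1.1, where false cases would raise the predicted incidence even if they had nothing to do with diet.

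This point is about when the replacement took place. Whether a replacement done during follow-up should need a fracture code is a separate question.

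**Working it through.** **1. Is the gap closed elsewhere in the SAP?**

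| Place | What it does | Does it catch a prior replacement coded later? |
|---|---|---|
| Section 2.1 | Excludes prior hip fracture and osteoporosis | Only if hip fracture is read to include replacement, which is not stated |
| Section 4 | Calls the outcome an incidence and times it from study entry | Shows the intent, but gives no first-event or operation-date rule |
| Section 7.1.1 | The likely confounders end with "menopausal status, chronic disease at baseline, and fracture at baseline (non-hip") | No; prior hip replacement is not named |
| Section 7.3 | A sensitivity analysis "excluding cases occurring in the first five years of follow-up (to check for reverse causality") | No, if the code first appears after year five |
| Supplementary Table 2 | Lists the covariates | No; prior hip replacement is not among them |

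**2. The plan's own figures.** Section 5 estimates power "assuming a sample size of 26,300 (after applying exclusion criteria") and with a 3% probability of hip fracture.

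- Planned events: 26,300 × 0.03 = 789.
- Minimum detectable hazard ratio for dietary group, with SD 0.36, two-sided 0.05 and 80% power: exp[(1.960 + 0.842) / (0.36 × √789)] = exp(2.802 / 10.11) = 1.319. Table 2 gives 1.32, so it reproduces.

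This is background only. The point does not dispute Table 2.

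**3. Number of false cases.** The SAP gives neither the prevalence of prior replacement nor the chance that an old replacement is coded at a later admission. Both inputs below are assumptions.

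False cases = 26,300 × prevalence × proportion coded later.

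| Prevalence (assumed) | Coded later (assumed) | False cases | Relative to 789 |
|---|---|---|---|
| 0.5% | 30% | 39 | 5% |
| 0.5% | 60% | 79 | 10% |
| 1% | 30% | 79 | 10% |
| 1% | 60% | 158 | 20% |
| any | 0% (code only at the operation) | 0 | 0% |

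The result depends heavily on these inputs. Prevalences of 0.5% to 3% with 10% to 100% coded later would give from 13 (26,300 × 0.005 × 0.10) to 789 (26,300 × 0.03 × 1.00) false cases.

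**4. Effect on a hazard ratio, one illustration.** Take 1% prevalence, half coded later, and false cases unrelated to diet.

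- False cases: 26,300 × 0.01 × 0.5 = 131.5, which is 131.5 / (789 + 131.5) = 14% of all counted cases.
- Vegetarian share: SD = √[p(1 − p)] = 0.36 gives p = 0.153.
- With a true hazard ratio of 1.32, the true cases among vegetarians are 789 × (0.153 × 1.32) / (0.153 × 1.32 + 0.847) = 151.9, and among the others 789 − 151.9 = 637.1.
- Adding the false cases in proportion (20.1 and 111.4), the observed ratio is about [(151.9 + 20.1) / 0.153] / [(637.1 + 111.4) / 0.847] = 1.27.
- Power at 920.5 counted events: Φ(0.36 × √920.5 × ln 1.272 − 1.960) = Φ(0.67) = 75%, against 80% planned.

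**The case against.** **Section 2.1 may already cover it.** Section 4 does not make replacement a separate outcome; it makes it a way of identifying a hip fracture. On that reading, hip fracture in section 2.1 includes a fracture identified by replacement. The outcome is also called an incidence and is timed by age at the event, so new events are plainly intended. This reading is possible, and it is why the point is put as *can be counted*. But the SAP never says that the section 4 definition governs section 2.1, and two analysts could build different cohorts from the same text.

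**The effect may be nil.** A false case arises only if the code for an old replacement surfaces at a later admission. The SAP does not describe how the code is recorded in the linked data. This stands: the number may be near zero. A reader might infer that pre-recruitment replacements will certainly be counted as outcomes, and the document does not support that.

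**Bias between diet groups.** A reader might also infer that the error differs by diet group, because prior replacement follows age and body weight. The SAP says nothing about who has replacements. Section 7.1.1 lists both age and BMI as likely confounders, so part of any such difference would be adjusted away. Adjustment does not repair a wrongly dated event, but a differential bias is not shown.

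**Exclusion is a choice.** A woman with one replaced hip can still fracture the other, so removing her is not the only defensible design. That is fair. What is needed is that the entry rule and the case rule agree.

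**It follows from a wider issue.** If section 4 required an accompanying fracture record, an old replacement coded later would not by itself make a case. That is true, but as written neither safeguard is present.

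**Conclusion.** The point holds as a mismatch between two definitions. Section 4 admits a replacement code as a case without requiring it to be new. Section 2.1 does not name prior replacement, and neither the listed covariates nor the five-year sensitivity analysis reliably catches it.

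The size is unknown. With 0.5% to 1% prior replacement and 30% to 60% coded later, there would be about 39 to 158 false cases against 789 planned events (5% to 20%). If the code is recorded only at the operation, there would be almost none. The fall in hazard ratio from 1.32 to 1.27, and in power from 80% to 75%, belongs to the single illustration above and assumes false cases unrelated to diet. None of this shows that results will be materially biased or that the error differs by diet. It shows that the written rule allows a wrongly dated event in the primary outcome, and that this can be closed cheaply before analysis.

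**What to change.** - **Section 2.1:** add hip replacement to the last criterion, so that it covers hip fracture, hip replacement or osteoporosis up to and including the recruitment date. Keep osteoporosis; nothing here argues for dropping it.
- **Section 2.1:** state that the section 4 code list is applied to all baseline and earlier hospital records held, so that prior events are found by the same definition as later ones.
- **Section 4:** state that a replacement code alone counts as a case only when the linked record shows that the operation took place after recruitment, and not when the code merely appears at a later admission. Name the record or field that supplies the operation date.

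The cost is a few sentences in the SAP. Slightly fewer women and events will remain, with a correspondingly small loss of precision. The number of women removed and the number of replacement-only codes not counted can be reported with the data-cleaning record that section 2 already promises, and this would show the actual size of the problem.

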3.1 Primary and secondary exposures

The primary exposures of interest are data-derived dietary group (regular meat-eater, occasional meat-eater, pescatarian, vegetarian, or vegan – see Table 1 for definitions) and dietary intake of foods, beverages, and nutrients, including: 1) fruits and vegetables; 2) animal products including meat, fish, eggs and dairy products; 3) tea and coffee, and 4) nutrients associated with hip fracture in previously published studies (protein, calcium, and vitamin D).

Secondary exposures of interest include self-identified dietary group (meat-eater, pescatarian, vegetarian, or vegan), types of meat (unprocessed red, all processed meat, and unprocessed poultry) and dairy products (milk, yoghurt, cheese, cream, and dairy desserts), caffeinated and decaffeinated coffee, and nutrients with a plausible association with hip fracture (such as phosphorus intake). All relevant exposures and their derivation are listed in Supplementary Table 1.

Table 1: Data-derived dietary group categories and definitions.

Dietary group	Definition
Regular meat-eater	Total meat intake ≥ 0.8 servings/day

Occasional meat-eater	Total meat intake < 0.8 servings/day & > 0.02 servings/day
Pescatarian	Total meat intake ≤ 0.02 servings/day & total fish intake > 0.02 servings/day
Vegetarian	Total meat and fish intakes ≤ 0.02 servings/day, intake of any dairy products or eggs > 0.02 servings/day
Vegan	Total meat, total fish, dairy products, and eggs intake ≤ 0.02 servings/day

Participants with consumption frequencies ≤ 0.02 servings/day (less than once a month) will be considered non-consumers.

3.2 Exposure assessment

Dietary information of the cohort was ascertained by a self-administered 217-item food frequency questionnaire (FFQ) [1]. The FFQ was validated by comparison with 4-d weighed food diaries and a repeated FFQ on 283 women three years after baseline [1].

The baseline questionnaire asked if participants identify as a meat-eater, vegetarian, or vegan – this will constitute the self-identified dietary group variable. It also included questions about consumption of foods and beverages in the form of ‘how often do you eat [specific food or beverage]?’ or similar. Ten responses were possible: 0 ‘never’, 1 ‘< once per month’, 2 ‘1-3 per month’, 3 ‘once per week’, 4 ‘2-4 per week’, 5 ‘5-6 per week’, 6 ‘once per day’, 7 ‘2-3 per day’, 8 ‘4-5 per day’, or 9 ‘6+ per day’. We will convert the responses to these questions into daily-based consumption frequencies as follows: 0, 0.02, 0.07, 0.14, 0.4, 0.8, 1, 2.5, 4.5, 6 times per day. Each exposure variable of interest will then be calculated in servings per day by summing daily consumptions of relevant items. For example, we will sum daily consumptions of unprocessed beef, pork, and lamb into one group titled ‘red meat’; questions on unprocessed chicken or turkey into ‘unprocessed poultry’; and questions around processed red or white meat or poultry into ‘processed meat’. Red meat, unprocessed poultry, and processed meat will be summed to form ‘total meat’. Similarly, questions on fish intake will be summed to calculate oily fish, non-oily fish, and total fish intakes; and questions on intake of dairy products will be summed to calculate milk, yogurt, cheese, cream, dairy desserts, and total dairy intakes in servings per day. Meat, fish, eggs and dairy exposures will then be used to classify subjects as regular meat-eaters, occasional meat-eaters, pescatarians, vegetarians, or vegans (Table 1). Due to the small number of vegans, vegetarians and vegans will be combined in the main analysis and considered separately in sensitivity analyses.

To explore potential associations between foods and beverages and hip fracture incidence, food and beverage intake variables in grams per day will be calculated by multiplying servings per day intake variables by standard portion weights, and summing relevant FFQ items. Food and beverage intake variables (grams/day) will be used to explore the effects of increment increases in intake on hip fracture risk, and to categorise participants into non-consumers (if > 1000 participants in this category) and levels of intake for all exposure variables, ensuring equal distribution of the population size among categories where possible. For intakes of milk, tea, coffee, and tea and coffee combined, increment increases and categories of intake will be defined by glasses and cups per day using standard sizes with the lowest exposure category as the reference group. For fruits, vegetables, and fruits and vegetables combined, categories will be defined to compare intakes below and above the

recommended five-a-day (400 g/day) intake, which will be used as the reference category. All other food and beverage exposures will be split into thirds or quarters.

Nutrient variables will be derived by multiplying food and beverage intakes (g/day) by nutrient concentrations in each food or beverage item using McCance and Widdowson’s Food Composition database (5th edition) [2].

4. Outcomes

Participants will be followed up via record linkage to the NHS Hospital Episode Statistics up to 31 March 2019. The primary outcome will be hip fracture incidence (International Classification of Diseases, ICD-9 code 820, and ICD-10 codes S72-S72.2). Hip fracture cases will also be identified by hip replacements (ICD-10 code Z96.64). The timeframe will be person years until hip fracture incidence (or until end of study period or death in those without a hip fracture), calculated as age at time of event (or non-event) minus age at study entry.

5. Sample size

The minimum detectable hazard ratio for the potential association between each primary exposure and hip fracture was estimated assuming a sample size of 26,300 (after applying exclusion criteria), an overall probability of hip fracture incidence of 3%, $p < 0.05$, and 80% power. For the dietary group analysis, a theoretical standard deviation of the exposure was calculated based on the percentage of participants in each category (Table 2). The minimum detectable effect of other primary exposures was calculated per standard portion size increase in intake using standard deviations of each exposure from the data in hand. Standard portion sizes were estimated from the Foods Standards Agency and previous UKWCS analyses [3, 4]. A standard portion size for total animal products was calculated by averaging standard servings of meat, fish, eggs, and dairy products.

Table 2: Minimal detectable hazard ratios for associations between primary exposures and hip fracture risk.

Exposure	SD	Minimum detectable HR
Dietary group (vegetarians vs non-vegetarians)	0.36	1.32
Fruit and vegetables (per 80 g increase)	300 g	0.98
Fruits (per 80 g increase)	227 g	0.97
Vegetables (per 80 g increase)	139 g	0.95
Total animal products (per 120 g increase)	248 g	0.95
Total meat (per 150 g increase)	81.2 g	0.84
Total fish (per 140 g increase)	28.3 g	0.61
Eggs (per 88 g increase)	18.6 g	0.63
Total dairy (per 105 g increase)	214 g	0.95

Tea and coffee (per cup increase)	2.17 cups	0.96
Tea (per cup increase)	2.01 cups	0.95
Coffee (per cup increase)	1.65 cups	1.06
Protein (per 25 g increase)	26.3 g	0.91
Calcium (per 300 mg increase)	365 mg	0.91
Vitamin D (per μg increase)	1.67 μg	0.94

1 cup of tea or coffee = 260 ml. SD = Standard deviation. HR = Hazard ratio. The SD for dietary group is theoretical and has arbitrary units.

6. Descriptive statistics

Baseline socio-demographic, anthropometric, diet, and lifestyle characteristics of the cohort were collected via questionnaire at baseline, and will be summarised (e.g. presenting their means and standard deviations) by: 1) dietary group (both for data-derived and self-identified dietary group); 2) total fruit and vegetable consumption; 3) total animal product consumption; 4) total tea and coffee consumption, and 5) protein, calcium, and vitamin D intakes, to report any differences in covariates (including co-exposures) between groups at baseline.

7. Statistical modelling

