7.1 Main analyses

We will fit Cox proportional hazard regression models to estimate the hazard ratios (HR) and 95% confidence intervals (95% CI) for associations between 1) the dietary groups and hip fracture incidence, with regular meat-eaters as the reference group; and 2) between intake of: fruits, vegetables, fruits and vegetables combined, total animal products, meat, fish, dairy, eggs, tea, coffee, tea and coffee combined, total protein, calcium, and vitamin D and hip fracture incidence. Each primary food, beverage, and nutrient exposure variable will be modelled as both categorical and continuous so that models can be fit comparing the risk of hip fracture between categories of intakes (where the target estimand is the relative causal effect of the exposure on hip fracture risk) and per increment increase in exposure intake (where the target estimand is the total causal effect of the exposure on hip fracture risk). We will also assess HR's for hip fracture as a function of primary exposure intake (non-linear dose-response) via restricted cubic splines for intake of: fruits, vegetables, fruits and vegetables combined, tea, coffee, and tea and coffee combined, since previous studies have shown non-linear relationships between each of these variables and hip fracture risk [5, 6]. Proportional hazards assumptions will be assessed based on Schoenfeld residuals.

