To estimate the population impact of diet on hip fracture incidence, we will determine the absolute risk difference for hip fracture between dietary groups and categories of exposure intakes, respectively. Predicted incidences and absolute risk differences will be calculated per 1000 person years and per 1000 people over 10 years using hazard ratios and 95% confidence intervals expressed as floating absolute risks [10].

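### A hip replacement code alone makes a woman a hip fracture case, and no fracture-code-only analysis would show the effect

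*SAP*

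**What the plan says.** Section 4 gives the fracture codes first: "The primary outcome will be hip fracture incidence (International Classification of Diseases, ICD-9 code 820, and ICD-10 codes S72-S72.2". The next sentence widens case-finding: "Hip fracture cases will also be identified by hip replacements (ICD-10 code Z96.64". It sets no co-recorded fracture code, admission type or time window. The same section fixes person-time: "The timeframe will be person years until hip fracture incidence (or until end of study period or death in those without a hip fracture". No other outcome is defined in the SAP.

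Section 7.1 states the target for the categorical food, beverage and nutrient models ("where the target estimand is the relative causal effect of the exposure on hip fracture risk") and for the continuous ones ("where the target estimand is the total causal effect of the exposure on hip fracture risk"). The dietary-group models are also for hip fracture incidence. Section 7.1.1 builds its causal diagrams for hip fracture and ends with absolute measures: "Predicted incidences and absolute risk differences will be calculated per 1000 person years", and also per 1000 people over 10 years.

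Section 5 bases the detectable effects on "an overall probability of hip fracture incidence of 3" per cent. It does not say whether replacement-only cases are in that figure. The one case-dropping analysis in section 7.3 works by time: "Additional sensitivity analyses will involve excluding cases occurring in the first five years of follow-up".

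**The concern.** A woman with a fracture code is already a case, so the replacement sentence changes something only for women without one. These women may be of two kinds: true fractures whose fracture code is missing, and replacements done for another reason. That the second kind exists is general knowledge, and no figure here rests on how common it is. The SAP has no rule to separate the two.

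To the extent that the second kind is counted, three things follow.

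- Each hazard ratio becomes a mixture of the fracture hazard ratio and the non-fracture-replacement hazard ratio. It is unbiased for fracture only if the two are equal.
- The predicted incidences at the end of section 7.1.1 are too high as hip fracture incidences.
- A woman counted through a non-fracture replacement stops contributing person-time, so a later true fracture in her is never counted.

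The outcome enters every model, and no planned output would let a reader judge how much this matters.

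**Working it through.** **Reproducing the plan's own figure.** Inputs from section 5 and Table 2: 26,300 women, 3% events, 80% power, SD 0.36 for dietary group. The two-sided 0.05 level is in section 7.3. Events D = 26,300 × 0.03 = 789. The minimum detectable HR is exp[(1.96 + 0.8416) / (0.36 × √789)] = 1.319, against 1.32 in Table 2. It reproduces. Below, 1.32 serves only as a scale for a true effect.

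**Is there a fracture-code-only analysis anywhere?** Section 7.2 covers subgroups and finer exposure types. Section 7.3 covers vegans separated from vegetarians, self-identified groups, mediators, BMI adjustment, phase two diet, early cases and long-term treatment. None selects cases by outcome code. Section 7.3 promises to present all analyses performed, but that does not help because this one is not planned.

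**Assumed quantities (not in the SAP).**

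- s: share of reference-group cases found by the replacement code alone, 10% to 30%.
- f: fraction of those that are not fractures, 0 to 1.
- HR_r: hazard ratio for non-fracture replacement, 0.8, 1.0 or 1.5.
- n = s × f, taken as constant over time.

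**Hazard ratio under section 4.** The two event rates add, so HR_obs = (1 − n) × 1.32 + n × HR_r.

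| n | HR_r = 0.8 | HR_r = 1.0 | HR_r = 1.5 |
|---|---|---|---|
| 0 | 1.32 | 1.32 | 1.32 |
| 0.05 | 1.294 | 1.304 | 1.329 |
| 0.10 | 1.268 | 1.288 | 1.338 |
| 0.15 | 1.242 | 1.272 | 1.347 |
| 0.30 | 1.164 | 1.224 | 1.374 |

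The bias can go either way. Under a fracture-code-only rule the hazard ratio stays at 1.32, provided that completeness of fracture coding does not vary by diet.

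**Incidence, counted over true.** Section 4 rule: 1 / (1 − s × f). Fracture-code-only rule: (1 − s) / (1 − s × f).

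| f | Section 4, s = 10% | Section 4, s = 30% | Fracture code only, s = 10% | Fracture code only, s = 30% |
|---|---|---|---|---|
| 0 | 1.00 | 1.00 | 0.90 | 0.70 |
| 0.5 | 1.05 | 1.18 | 0.95 | 0.82 |
| 1 | 1.11 | 1.43 | 1.00 | 1.00 |

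**Events and power.** Suppose the 789 events include replacement-only cases, with 10% to 30% now taken as a share of all events. Dropping them leaves 789 × 0.9 = 710 to 789 × 0.7 = 552. These are lower bounds, because women with a replacement stay at risk of a later fracture. The same formula gives a minimum detectable HR of 1.339 at 710 events and 1.393 at 552.

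Power for a true HR of 1.32 is 80% at 789 events. If the replacement-only cases are all non-fractures unrelated to diet, power under section 4 falls to 73% and 53% (observed HR 1.288 and 1.224). With the narrower definition it is 76% and 65%. If they are all true fractures, section 4 keeps 80% and the narrower definition has 76% and 65%.

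**The case against.** The strongest reply is that wide and narrow case-finding trade sensitivity against specificity, and the SAP does not show which is better here. Nothing in the document anchors s, f or HR_r. At f = 0 section 4 is exact and a fracture-code-only rule understates incidence at 0.90 to 0.70 of true. The two rules miss incidence by equal amounts at f = 0.5, and below that section 4 does better. The narrower rule's advantage for the hazard ratio also rests on an assumption, that coding completeness does not differ by diet. On this view a fracture-code-only sensitivity analysis with counts by route would be enough.

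The incidence point stands, and it is why incidences are needed under both definitions. For the hazard ratio, which is the main output, the two assumptions are not equally demanding. The fracture-code rule needs only coding completeness unrelated to diet. Section 4 needs every replacement-only case to be a fracture, or diet to act equally on fracture and on non-fracture replacement. The wide definition is kept as a sensitivity analysis, so its information is not lost.

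It can also be argued that a replacement before recruitment already falls under the prior-hip-fracture exclusion in section 2.1, if section 4's case definition is read into it. That reading is possible, but section 2.1 does not name replacement, so it should be stated.

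**Conclusion.** The point holds. As written, the only outcome can include events that are not hip fractures, the stated target is hip fracture risk, and nothing planned would show the difference. That much follows from the text alone.

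The size does not. On the assumed 10% to 30% share with f = 1, a true HR of 1.32 would be reported as 1.29 to 1.22 if replacement is unrelated to diet. It would be 1.27 to 1.16 if the replacement HR is 0.8, and 1.34 to 1.37 if it is 1.5. With f = 0.5 and no relation to diet it would be 1.30 to 1.27. With f = 0 there is no bias in either the hazard ratio or the incidence. Because the definition feeds every model and is cheap to correct, it should be changed before the analysis is run.

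**What to change.** - Define the primary outcome by a recorded hip fracture code (ICD-9 820 or the ICD-10 fracture codes in section 4), and drop replacement alone as a route to case status.
- Keep fracture-or-replacement as a labelled sensitivity analysis in section 7.3, excluding women with a hip replacement before recruitment.
- Report the number of replacement-only cases, and give the section 7.1.1 incidences and risk differences under both definitions.
- State in section 5 whether the 3% includes replacement-only cases, and restate Table 2 if it does.

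The work is a change of wording, a change to the case-definition code and one extra sensitivity run. The downsides are fewer counted events and missed true fractures where only the replacement was coded. Such misses lower the incidences but leave the hazard ratio unbiased if coding completeness is similar across diet groups. If the 3% already includes replacement-only cases at the assumed 10% to 30%, the dietary-group minimum detectable HR rises from 1.32 to at most 1.34 to 1.39. Otherwise it is unchanged.
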